7.1 Criteria for Dosing Modifications

(For Phase II part we suggest the following dose reduction schedule as incorporated in other ongoing studies)

Investigators can use their discretion when making dose-reduction decisions for ICE based on the package insert recommendations unless otherwise specified in the guidelines in Table 7-1 below. In addition Patients should be discontinued from study treatment if they require a dose delay > 14 days from the intended day of the next scheduled dose (for all events other than prolonged QTcF). If a patient cannot be dosed due to prolonged QTcF interval for more than 7 days since last dose, patient should be discontinued from study. All cardiac events should be treated as per the local standard of care and referred to a specialist by the investigator if clinically indicated. Any final decisions concerning any dose modification / interruptions or patient discontinuing study drug permanently should be made by the investigator based on QTcF calculations assessed. Nothing in this protocol or the underlying agreement shall be deemed to restrict or interfere with the independent medical judgment and decision making abilities of the investigator or other M.D. Anderson personnel.

Table 7-1 Criteria for dosing delays, dose-reductions, and re-initiation of treatment due to study drug-related toxicity (excluding QT prolongation) (only applies to Phase II)

Worst Toxicity CTCAE Grade**** unless otherwise specified (Value)		Dose Modification Guidelines At any time during a cycle of therapy (including intended day of dosing)*
HEMATOLOGICAL TOXICITIES		
Thrombocytopenia	Grade 4 (< 25 x 10 ⁹ /L)	Temporarily discontinue panobinostat dosing until resolved to ≤ grade 2, or baseline, then: 
 restart panobinostat reduced by one dose level If event recurs, hold drug and resume at next lower dose level*
Neutropenia (ANC)	Grade 4 (ANC < 0.5 x 10 ⁹ /L)	Temporarily discontinue panobinostat dosing until resolved to ≤ grade 3, or baseline, then: 
 Restart panobinostat reduced by one dose level If event recurs, hold drug and resume at next lower dose level*
	Febrile neutropenia (ANC < 1.0 x 10 ⁹ /L, fever ≥ 38.5°C)	Temporarily discontinue panobinostat dosing until fever resolved and ANC ≤ grade 2, then restart panobinostat reduced by one dose level
NON-HEMATOLOGICAL TOXICITIES		
CARDIAC		
Cardiac - Prolonged QT interval**		Please refer to Section 7.2
GASTROINTESTINAL		
Diarrhea	Grade 2 (4-6 stools/day over baseline, etc) despite the use of optimal antidiarrheal medications	Temporarily discontinue panobinostat dosing until resolved to ≤ grade 1, or baseline, then restart at an unchanged dose level 
 If event recurs, hold drug and resume at next lower dose level*
	Grade 3 (≥ 7 stools/day over baseline, etc) despite the use of optimal antidiarrheal medications	Temporarily discontinue panobinostat dosing until resolved to ≤ grade 1, or baseline, then restart panobinostat reduced by one dose level 
 If event recurs, hold drug and resume at next lower dose level*
	Grade 4 (life-threatening consequences, hemodynamic collapse, etc) despite the use of optimal antidiarrheal medications	Discontinue panobinostat dosing
Vomiting/Nausea***	Grade 1 & 2 not requiring treatment or controlled using standard anti-emetics	Maintain dose level
	Grade 3 or 4 vomiting or Grade 3 nausea that cannot be controlled despite the use of standard anti-emetics	Temporarily discontinue panobinostat dosing until resolved to ≤ grade 1, or baseline, then restart panobinostat reduced by one dose level 
 If event recurs, hold drug and resume at next lower dose level*
Fatigue		

Worst Toxicity CTCAE Grade**** unless otherwise specified (Value)		Dose Modification Guidelines At any time during a cycle of therapy (including intended day of dosing)*
Fatigue	Grade 3 or 4	Temporarily discontinue panobinostat dosing until resolved to \leq grade 2, or baseline, then: 
 • restart panobinostat reduced by one dose level • If event recurs, hold drug and resume at next lower dose level*
HEPATIC		
Total Bilirubin	Grade 3 or 4	Temporarily discontinue panobinostat dosing until resolved to \leq grade 2, or baseline, then restart panobinostat reduced by one dose level
Note: If Grade 3 or Grade 4 hyperbilirubinemia is due to the indirect component only, and hemolysis as the etiology has been ruled out as per institutional guidelines (e.g., review of peripheral blood smear and haptoglobin determination), then reduction of one dose level and continuation of treatment is at the discretion of the Investigator.		
AST/SGOT, ALT/SGPT	> 5-10 x ULN	Temporarily discontinue panobinostat dosing until resolved to \leq grade 1 or baseline, then restart at an unchanged dose level 
 • If event recurs, hold drug and resume at next lower dose level*
	> 10 x ULN	Temporarily discontinue panobinostat dosing until resolved to \leq grade 1, or baseline, then: 
 • restart panobinostat reduced by one dose level • If event recurs, hold drug and resume at next lower dose level*

All dose modifications should be based on the worst preceding toxicity.
 
* For each dose reduction, should the event recur after resuming drug, further dose reductions are permitted
 
** It is critical that electrolyte abnormalities be followed closely and corrected prior to dosing
 
*** See also concomitant medication section 7.3
 
**** Common Terminology Criteria for Adverse Events (CTCAE Version 4.0)
		

General guidelines for dose modifications due to adverse events related to study drug are provided below.

Grade 3 or 4 non-hematologic toxicity

Patients experiencing new (or treatment emergent) CTCAE grade 3 or 4 non-hematologic AEs not listed in [Table 7-1](#), should have their treatment temporarily discontinued until the adverse event resolves to \leq CTCAE grade 1 or baseline unless otherwise specified in [Table 7-1](#). If the AE was considered related to panobinostat, the drug should then be restarted at one dose level lower. If the AE was considered not related to panobinostat, then therapy may be restarted (when the AE resolves to \leq grade 1 or baseline) at the current dose and schedule

Management of diarrhea

Patients should be instructed to contact their physician at the onset of diarrhea. Each patient should be instructed to have loperamide readily available and to begin treatment for diarrhea at the first episode of poorly formed or loose stools or the earliest onset of bowel movements more frequent than normally expected for the patient.

Loperamide 4 mg should be taken at the first loose stool or more frequent than usual bowel movements, followed by 2 mg as needed, no more frequently than every 4 hours, not to exceed a total of 16 mg in 24 hours. Patients with diarrhea \geq grade 2 despite this loperamide regimen should interrupt treatment with panobinostat as described in [Table 7-1](#). If the above regimen is inadequate then additional evaluation and treatment should be pursued as medically indicated. Replacement i.v. fluids and electrolytes may be used as appropriate. Additional treatment should be provided in accordance with institutional standard of care and/or local guidelines.

Premedication with loperamide is not recommended.

The use of drugs with laxative properties should be avoided because of the potential for exacerbation of diarrhea. Patients should be advised to contact their physician to discuss any laxative use.

7.2 Dose modifications for prolonged QTcF interval

All cardiac events should be treated as per the local standard of care and referred to a specialist if clinically indicated. Any final decisions concerning dose modifications or permanently discontinuing the patient from study drug due to QTcF prolongation will be based on the assessment of the Investigator. Any plan to deviate from these guidelines should be previously discussed and agreed upon by the investigator. If a patient cannot be dosed due to prolonged QTcF for more than 7 days since last dose, patient should be discontinued from study.

Table 7-2 Criteria for dosing delays, dose-reductions, and re-initiation of treatment due to study drug-related QTcF abnormalities

ECGs to be performed at specified time point	Abnormality Noted	Dose Modification Guideline - At any time during a cycle of therapy (including intended day of dosing)
Cycle 1 dose modifications		
Pre-dose for each cycle on day 1 for cycle 2 and 3 and for day -6 and -2 on cycle 1 only:	If Day 1 for cycles 2 and 3 and day -6 and -2 for cycle 1 only: A single ECG obtained shows QTcF > 460 msec	
Check and correct the patient's serum potassium, magnesium, calcium and phosphorus immediately, as well as evaluate con-meds.
 
Notify Investigator immediately for prompt review.
 
If abnormality noted on Day 1 of Cycle 2 and 3 and day -6 and -2 for cycle 1 only:
 
Delay dose at least 3 days and repeat pre-dose ECG. If the pre-dose ECG:
 
Do not meet criteria again, discontinue patient from study.
 
Do meet criteria for dosing; administer study drug treatment at.
 
Do meet pre-dose ECG criteria for dosing and QT prolongation determined to be related to study drug, resume study drug treatment with a dose reduction of 10 mg. If however, it was determined that the QT prolongation was secondary to electrolyte abnormalities or con-meds, continue at the same dose level. Repeat ECGs - pre-dose (x3), 3-hours post-dose (x3), and 6-hours post-dose (x3) on the next scheduled dosing day after the reduced dose is given.*

	A single ECG obtained shows QTcF >480 msec to \geq 500 msec	
Check and correct the patient's serum potassium, magnesium, calcium and phosphorus immediately.
 
Notify Investigator immediately for prompt review. Discontinue patient from study therapy

Cycle 1 day -6 and -2 only, post-dose:	A single post-dose ECG obtained shows QTcF \geq 480 msec to $<$ 500 msec OR > 60 msec increase from baseline	
If abnormality noted on Day 6 or -2 of Cycle 1 (post- dose):
 
Check and correct the patient's serum potassium, magnesium, calcium and phosphorus immediately, as well as evaluate con-meds.
 
Monitor ECG hourly or by telemetry until at least 2 consecutive hourly ECGs performed at least 6 hours post dose are $<$480.
 
Notify Investigator immediately for prompt review. Delay dose 3 days and repeat pre-dose ECG.
 
If the pre-dose ECG:
 
Do not meet pre-dose ECG criteria for dosing (pre-dose ECGs have a QTcF \leq 460 msec), discontinue patient from study.
 
Do meet pre-dose ECG criteria for dosing (pre-dose ECGs have a QTcF \leq 460 msec) and QT prolongation determined to be related to study drug, resume study drug treatment with a dose reduction of 10 mg. If however, it was determined that the QT prolongation was secondary to electrolyte abnormalities or con-meds, continue at the same dose level. Repeat ECGs - pre-dose (x3), 3-hours post-dose (x3), and 6-hours post-dose (x3) on the next scheduled dosing day after the reduced dose is given*.

	A single ECG obtained shows QTcF \geq 500 msec	
Check and correct the patient's serum potassium, magnesium, calcium and phosphorus immediately.
 
Notify Investigator immediately for prompt review.
 
Discontinue patient from study therapy

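### Table 7-2: the pre-dose delay row (QTcF above 460 msec) has no upper limit, so it overlaps the pre-dose discontinue row, and no text says which governs once QTcF recovers

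*Combined protocol and SAP*

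**What the plan says.** Table 7-2 has two pre-dose rows, for days -6 and -2 of cycle 1 and day 1 of cycles 2 and 3.

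- **First pre-dose row.** Trigger: "A single ECG obtained shows QTcF > 460 msec", with no ceiling. Action: "Delay dose at least 3 days and repeat pre-dose ECG". If the repeat fails the dosing criterion, the patient is discontinued. If it passes, panobinostat resumes, 10 mg lower when the prolongation is judged drug-related, or at the same dose when electrolytes or other medicines explain it.
- **Second pre-dose row.** It starts at about 480 msec. Action: "Notify Investigator immediately for prompt review. Discontinue patient from study therapy". No repeat ECG or recovery path is given.

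The post-dose rows, for cycle 1 days -6 and -2, are as follows.

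- **Delay row.** "A single post-dose ECG obtained shows QTcF" of 480 to below 500 msec, "OR > 60 msec increase from baseline". Dosing is held 3 days and may restart if the patient qualifies: "Do meet pre-dose ECG criteria for dosing (pre-dose ECGs have a QTcF" of 460 msec or less).
- **Discontinue row.** QTcF of 500 msec or more.

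The text of Section 7.2 leaves final decisions to the Investigator. It also discontinues a patient who "cannot be dosed due to prolonged QTcF for more than 7 days since last dose".

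**The concern.** A stopping threshold for a recognised cardiac risk should give one answer for one reading. Here, every pre-dose value that meets the discontinue row also meets the delay row.

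The two rows agree if QTcF stays above 460 msec, because both then end in discontinuation. They disagree if QTcF recovers to 460 msec or less: the first row restarts panobinostat and the second stops it for good. Two investigators could treat the same patient in opposite ways, and neither could be shown to have deviated from the protocol.

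The post-dose rows have a smaller version of the same problem. A reading of 500 msec or more calls for discontinuation, but if it is also more than 60 msec above baseline it meets the delay row too.

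**Working it through.** **1. Pre-dose rows side by side.** The first row is taken as printed (above 460 msec) and the second under alternative readings of its limits.

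| Second row read as | Values meeting both rows (whole msec) | Overlap if first row stops at 480 |
|---|---|---|
| above 480, no upper limit | 481 and up | none |
| above 480 to 500 inclusive | 481 to 500 | none |
| 480 or more, no upper limit | 480 and up | 480 only |
| 500 or more | 500 and up | none |

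Under each reading the second row lies wholly inside the first, so the overlap comes from the first row's missing ceiling. Ending the first row at 480 and starting the second above 480 removes it.

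**2. What happens next.** Take a pre-dose reading of 490 msec, with the second row starting above 480.

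- Repeat ECG above 460: first row discontinues, second row discontinues. No conflict.
- Repeat ECG 460 or less: first row resumes, second row discontinues. Conflict.

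**3. Possible tie-breakers.**

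- The Investigator clause in Section 7.2 says who decides, not which row applies.
- The note that modifications follow the worst preceding toxicity belongs to Table 7-1, whose title limits it to changes "due to study drug-related toxicity (excluding QT prolongation) (only applies to Phase II"). It does not reach QT events.
- The 7-day limit concerns a patient who cannot be dosed. It does not address one who recovers in time.

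**4. Can the conflict arise within the 7-day limit?** Yes, at cycle 1 day -2. The previous dose is on day -4 (Tables 5.1 and 5.1.1). A 3-day delay from day -2 gives day 1, since the schedule includes day 0. The gap is 1 - (-4) = 5 days. Day -6 precedes any panobinostat, and cycle 3 contains none. Cycle 2 day 1 depends on the schedule. Under Schedule B the last dose is day 5 and cycle 2 starts on day 15, so 15 - 5 = 10 days have already passed, and a literal count may discontinue the patient anyway. Under Schedule A the last dose is day 12, so a 3-day delay restarts at 18 - 12 = 6 days.

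**5. Post-dose overlap.** Exclusion criterion 12 removes patients with a screening QTc above 450 msec. If that ECG is the baseline and the same correction is used (assumptions), any post-dose reading above 450 + 60 = 510 msec is more than 60 msec above baseline and meets both post-dose rows.

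**6. Size.** Inputs are the 20 and 30 mg columns of Table 1-3 and the average panobinostat-arm sizes in Section 10.0. Each patient is assumed to be counted once, by highest value.

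- Patients with a QTcF value: 102 + 9 = 111.
- Any QTcF above 480 msec: 3 (above 480 to 500) + 1 (above 500) = 4, all at 20 mg.
- 4/111 = 3.6%, exact 95% CI 1.0% to 9.0%.
- Panobinostat-arm size: 25.7 (scenario 3) to 32.8 (scenario 2).
- 25.7 × 4/111 = 0.93; 32.8 × 4/111 = 1.18.

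The title of Table 7-2 does not restrict it to phase II. If it also covers the 10-patient Schedule B expansion cohort, add 10 × 4/111 = 0.36.

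These figures are ceilings. They count a high reading at any time under intensive pre- and post-dose monitoring. The conflict needs a pre-dose reading at a relevant check, followed by recovery.

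**The case against.** The strongest reply is that the table is easily read as intended. If the first row governed after recovery, the second row's immediate discontinuation would never have a separate effect, so the stricter row must override it. That is how stepped toxicity tables are normally read, and most investigators would do so. The post-dose rows concern a reading about 2 hours after dosing, so a stricter rule for a pre-dose reading is coherent. Both pre-dose rows also require immediate notification of the Investigator, who has the final say.

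Much of this stands, and it is why the point is minor. It does not remove the gap. Precedence is inferred rather than stated, and because the same table permits restart after 480 to below 500 msec post-dose, a reader cannot be certain where the pre-dose stop was meant to begin.

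A reader might go further and infer that the second row's range is itself wrongly written, because it appears with two lower limits in the available text. The documents do not support that: the sign before 500 may have been misread from the PDF. It is not part of this point, and neither is the possible consequence that readings above 500 msec meet only the delay row.

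Table 7-2 also carries an asterisk whose note is absent from the available text. It is attached to the repeat-ECG instruction and probably does not set precedence, but that cannot be checked.

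**Conclusion.** The point holds as a low-severity correction to a safety table. The first pre-dose row lacks an upper limit, it overlaps the discontinue row, and no text in Sections 7.1 or 7.2 says which applies to a patient who recovers.

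The upper guide is about one panobinostat-arm patient (0.93 to 1.18). It rests on 4 of 111 patients in other panobinostat studies, on counting each patient once, and on rates at 20 to 30 mg carrying over; Table 1-3 has no 10 mg group. The documents do not say what share of such readings would be pre-dose at a relevant check and then recover, so no lower figure is offered.

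Two stronger inferences are not supported. The table does not allow dosing while QTcF is prolonged, since both pre-dose rows withhold panobinostat. Nor is there any effect on the complete-response comparison or its operating characteristics.

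**What to change.** In Table 7-2:

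- Write the first pre-dose trigger as QTcF above 460 and up to 480 msec.
- Write the second pre-dose trigger as QTcF above 480 msec with no upper limit. The clinical team should confirm 480 as the cut-off.
- Add one sentence: a post-dose QTcF of 500 msec or more means discontinuation even if it is also more than 60 msec above baseline.

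The cost is two table cells and one sentence in the next amendment, with no new procedures, visits or data.

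### Table 7-2's QTcF >460 msec row attaches panobinostat dose steps and removal from study to cycle 3 day 1, when no panobinostat is scheduled

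*Combined protocol and SAP*

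**What the plan says.** Sections 5.1.4 (phase I) and 5.2.4 (phase II) restrict panobinostat to the first two ICE cycles, and Table 5.2 repeats this. Section 5.2.4 gives the reason: to protect stem cell collection.

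The time-point column of Table 7-2's pre-dose row reads "Pre-dose for each cycle on day 1 for cycle 2 and 3 and for day -6 and -2 on cycle 1 only". The abnormality column names the same days, and the action column opens its dose steps with "If abnormality noted on Day 1 of Cycle 2 and 3". For a single QTcF above 460 msec the actions are:

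- correct "serum potassium, magnesium, calcium and phosphorus immediately, as well as evaluate con-meds", and notify the investigator;
- "Delay dose at least 3 days and repeat pre-dose ECG";
- if the repeat ECG fails: "Do not meet criteria again, discontinue patient from study";
- if it passes and the prolongation is drug-related: "resume study drug treatment with a dose reduction of 10 mg"; if electrolytes or other medication explain it, continue at the same dose.

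A second row under the same time points, for QTcF above 480 msec, has no delay step: "Notify Investigator immediately for prompt review. Discontinue patient from study therapy".

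Table 6-3 schedules the matching ECG on day 1 of cycle 2 and every later cycle. Sections 6.2 and 10.0 place the response assessment after three cycles of ICE.

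**The concern.** The row manages panobinostat dosing, but one of its named days falls after the last planned panobinostat dose. Electrolyte correction, medication review and notification remain sensible then. The 10 mg reduction and the resumption of study drug do not. The removal step is the one with consequences: followed literally, it ends study participation because of an ECG that no longer governs any panobinostat dose.

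At that moment the patient still has one of three ICE cycles to receive on study, and the response scan is still ahead. In phase II arm 2 that scan supplies the primary outcome. Section 9.2 asks for the end-of-study procedures at withdrawal, and the withdrawal visit in section 6.2.1 lists an examination and an EKG but no imaging. A patient removed here therefore has no scheduled response scan.

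**Working it through.** This is a consistency check. The plan states no figure to reproduce.

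**Step 1. Match each ECG point in the pre-dose row to a panobinostat dose** (Tables 5.1, 5.1.1 and 5.2; sections 5.1.4, 5.1.5, 5.2.3 and 5.2.4).

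| ECG point in Table 7-2 | Panobinostat due that day? |
|---|---|
| Cycle 1 day -6 | Yes |
| Cycle 1 day -2 | Yes |
| Cycle 2 day 1 | Yes |
| Cycle 3 day 1 | No |

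Three of the four points precede a dose; 4 - 3 = 1 does not.

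**Step 2. Count the doses left at cycle 3 day 1.** The lead-in from day -6 belongs to cycle 1 only.

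- Schedule B: cycle 1 days -6, -4, -2, 1, 3, 5 = 6; cycle 2 days 1, 3, 5 = 3; cycle 3 = 0. Total 6 + 3 = 9, so 0 of 9 remain.
- Schedule A: cycle 1 days -6, -4, -2, 1, 3, 5, 8, 10, 12 = 9; cycle 2 days 1, 3, 5, 8, 10, 12 = 6; cycle 3 = 0. Total 9 + 6 = 15, so 0 of 15 remain.

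ICE cycles still to give: 3 - 2 = 1.

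**Step 3. Test each action on cycle 3 day 1 under both meanings of dose.**

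| Action | If dose means panobinostat | If dose means ICE |
|---|---|---|
| Delay at least 3 days | Nothing to delay | Possible; outside the 2-day window of 5.2.6 but inside the 14-day allowance of 5.2.7 |
| Reduce by 10 mg | Nothing to reduce | No meaning: ICE is dosed in g/m², mg/m² and AUC |
| Resume study drug | Nothing to resume | ICE could proceed, but the step is written for study drug |
| Remove from study after a failed repeat | Arguably not reached, as no delay occurs; but the introducing line names cycle 3 | Reached; ends participation before cycle 3 and the scan |

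Neither meaning makes the whole row work.

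**Step 4. Look for text that resolves the conflict.** The sub-header above these rows refers to cycle 1 dose modifications, but the row beneath names cycles 2 and 3. Section 6.2.1 lets some patients who benefit continue on study, but only after three cycles, so it puts no panobinostat into cycle 3.

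**Step 5. Gauge the likelihood.** No rate is given for a repeated pre-dose QTcF above 460 msec at this point. Screening excludes QTc above 450 msec. Under Schedule B, which Table 5.2 shows for arm 2, the last planned dose is cycle 2 day 5. An on-time cycle 3 starts 15 - 5 = 10 days later, or 240 hours; at the mean half-life of about 15 hours in section 3.1, 240 / 15 = 16 half-lives. Section 3.1 also mentions a possible delayed QTcF effect, so the risk is not zero.

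**The case against.** The strongest reply is that dose can include ICE. The protocol elsewhere speaks of doses of ICE, so a pre-dose ECG on cycle 3 day 1 may simply precede ICE. A short hold would then make sense, and the 10 mg line would not apply. This stands for the delay and for the label in Table 6-3, which needs no correction. It does not rescue the 10 mg step, and on this reading the removal step is reached.

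The second reply is discretion. Section 7.2 says that final decisions on dose modification, or on permanently stopping study drug for QTcF, "will be based on the assessment of the Investigator", and it allows deviations agreed beforehand. Section 7.1 protects independent medical judgment, and the action column is headed as a guideline. This softens the point considerably. But the 7.2 clause concerns study drug, while the table's action is removal from the study.

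Third, section 6.2 keeps patients who stop early for toxicity evaluable for response. The patient is then not lost from the response population, though the scan may be.

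Fourth, one sentence in the cell is incomplete and a footnote is not visible in the public copy, so a qualifier could be missing. The time points and the steps discussed here are complete.

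A reader might go further and infer that the cycle 3 ECG is itself a mistake. The documents do not support that: Appendix 1 recommends close QT monitoring with 5HT3 antiemetics, and section 3.1 raises the possible delayed effect.

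**Conclusion.** The mismatch is certain; its practical effect is small. One of four ECG points carries reduction and resumption steps with no dose to act on, and a removal step that, read literally, could take a patient off study before ICE cycle 3 and the response scan. That harm assumes that staff follow the table literally and that the repeat ECG is also abnormal. Removal means that ICE cycle 3 is not given on study; the protocol does not forbid ICE elsewhere. **Severity: minor.**

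Three stronger inferences are not supported:

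- *A number of patients lost, or an effect on arm selection.* Table 1-3 gives single-agent, any-time QTcF data, not the rate of a repeated abnormal ECG after panobinostat has ended. No count can be derived.
- *Damage to the phase I primary outcome.* That outcome is the MTD, judged in the first treatment cycle (section 5.1.13). The primary-outcome consequence is confined to phase II arm 2.
- *An error in the >480 msec stop.* What is unclear there is only whether the therapy stopped at cycle 3 is panobinostat, with no effect, or ICE.

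**What to change.** In the >460 msec row of Table 7-2, limit the panobinostat delay, reduction, resumption and study-removal steps to cycle 1 days -6 and -2 and cycle 2 day 1.

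For cycle 3 day 1, keep the ECG as pre-ICE monitoring, with electrolyte correction, medication review and investigator review, including any short ICE hold within the existing 14-day allowance. State that the patient stays on study for ICE cycle 3 and the response scan unless the investigator judges ICE unsafe.

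In the >480 msec row, state only whether the therapy stopped at cycle 3 means panobinostat or ICE.

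The cost is a few words in one table, with no added procedures or patients. The one trade-off is that an automatic removal at >460 msec in cycle 3 becomes an investigator decision.
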